8.2 Risks**a. Potential risks (PHASE II Focus Group ONLY):**

Check boxes below for all potential study risks

- ☒ Discomfort at answering personal questions or psychological distress due to research procedures
- ☒ Breach of confidentiality
- ☐ Physical adverse effects from the following:
- ☐ Blood draw
- ☐ Clinical intervention, such as exercise program, in-person counseling
- ☐ Medical procedure, such as X-ray, strength measure, screening tests, etc.
- ☐ Medication(s) given as part of research
- ☐ Other (describe briefly): | |

a. Potential risks (PHASE III Intervention):

Check boxes below for all potential study risks

- ☐ Discomfort at answering personal questions or psychological distress due to research procedures
- ☒ Breach of confidentiality
- ☐ Physical adverse effects from the following:
- ☐ Blood draw
- ☐ Clinical intervention, such as exercise program, in-person counseling
- ☐ Medical procedure, such as X-ray, strength measure, screening tests, etc.
- ☐ Medication(s) given as part of research
- ☐ Other (describe briefly): | |

b. Unforeseeable Risks

Which procedures, if any, may have risks to the subjects that are currently unforeseeable? Explain

[NA]

c. Risks by Population

If any of the risks listed in above apply to only certain cases or subgroups within the study, please describe here.

[NA]

d. High-Risk Methods or Clinical Procedures

Does this study involve any high-risk methods or clinical procedures (e.g., investigational drugs, devices, or procedures; radiation exposure; or other intervention with patients, etc.)?

☐ YES ☒ NO

If YES, Describe the probability, magnitude, duration, and reversibility of the risks. Describe any physical, psychological, social, legal, and economic risks and how they will be managed?

[]

d. Coordination of Care with Provider(s)

Will the patient undergo any clinical procedures or receive any medications that might require coordination of care with the patient's health care provider(s)?

☐ YES ☒ NO

If YES, please briefly describe what steps you will take so the study participant's health care is not negatively affected (e.g., how you will track care to follow-up on a research intervention if needed, etc.)

[]

e. Sensitive Topics

Please check whether data will be collected on any of the following topics:

☐ Sensitive aspects of subjects' behavior, such as drug use, sexual behavior or use of alcohol

☐ Any information that could put subjects at risk of criminal or civil liability

☐ Any information that, if disclosed, would likely have negative consequences to the participants or damage their financial standing, employability, insurability or reputation

f. Reporting of Risk of Harm or Abuse

Indicate whether you are collecting, or are likely to learn incidentally, information about the following:

☐ Child abuse, elder abuse, or spouse abuse

☐ Risk of harm to self or others (i.e., suicidal ideation, threats to others)

If you checked either of these items, describe the reporting plan here and, if applicable, in the consent form.

[]

g. Incidental Findings

Does the study carry a risk of incidental findings?

**KPWA IRB Application
(Use with Core Data Form)**

Version Date: 11/06/2019

Page 47 of 56

☐ YES ☒ NO

If YES, describe your plan for evaluating these and determining whether and how subjects or their providers will be given this information.

[]

h. Previously Unknown Condition

Is it possible that you will discover a previously unknown condition (disease, genetic predisposition, etc.) in a subject as a result of study procedures?

☐ YES ☒ NO

If YES, explain how you will handle this situation:

[]

i. Electronic Communication(s) and Data Transmission

Will the internet, email, or any other electronic communication, be used to communicate with participants, OR collect and/or transmit data (other than de-identified datasets) inside or outside of KP Washington? (Examples include websites, software applications, smart phones, laptop computers, tablets, Fitbits, iPads, etc.)

☐ YES ☒ NO

If YES, Complete **Supplement B**.

If YES, how will you verify the participant's identity?

[]

9. Adverse & Unanticipated Events**9.1. Management of Adverse/Unanticipated Events**

Who will handle any adverse/unanticipated events for this study?

[KPWHRI PI, [name], and Project Manager [name] will handle any adverse/unanticipated events.]

9.2 Data Safety Monitoring Plan

Is a data safety monitoring (DSM) plan required by the sponsor or otherwise planned?

☐ YES ☒ NO

If YES, Describe the provisions for data and safety monitoring (DSM) to ensure safety of research participants. Please indicate the following details in your DSM plan:

- adverse event (AE) grading scale
- plan for unanticipated AE reporting
- plan for anticipated AE reporting
- plan for safety review (by whom and what frequency)
- plan for ongoing review of results (if appropriate)

[]

9.3 Data Safety Monitoring Board

Is a data and safety monitoring board (DSMB) required by the sponsor or otherwise planned?

☐ YES ☒ NO

If YES, provide details of the DSMB.

[]

9.4 Financial Responsibility for Injury

Guidance: Please make sure that the study contract and/or KP Washington policies support any language regarding physical injuries. If the study is greater than minimal risk, information about who is responsible for treatment of physical injuries caused by the study is required in the consent form.

a. Responsible Party

Who will be financially responsible for treatment of physical injuries resulting from study procedures?

- ☐ Study sponsor
☐ Subject or subject's insurer
☒ Not applicable
☐ Other, explain: []

b. Financial Responsibility and Consent Form

Does the consent form explain who will be financially responsible for treatment of physical injuries resulting from study procedures?

- ☒ Not applicable
☐ YES continue
☐ NO please explain: []

10. Privacy, Confidentiality, Data Storage, & Data Security

10.1 Subject Privacy During Participation

Describe the steps that will be taken to protect subject privacy during recruitment, consent and study procedures (e.g., will subjects be recruited in a private space, where will you keep written study materials, etc.)

Phase II (Focus Group): Patients will have privacy during our study recruitment and screening calls because they will be called at their preferred contact number. Our study staff will always ask if this is a good time for learning more about our study and answering question to see if he/she is eligible to participate in one of our focus groups. If the participant agrees to participate in the focus groups, informed consent will be administered individually in a private room adjacent to the focus group meeting room.

Phase II work was completed in 2019.

Phase III (Trial):

Opt-Out Protocol (July 2020-October 2020)

Study recruitment materials accompanied by a Study Information Sheet, will be mailed to individuals. Potential participants can choose to open the letter at a time that is appropriate for him/her. There are no recruitment or screening calls for this Phase. If a participant chooses to opt out of the study by calling our study line, the participant can choose to make that call at any time when it feels right for him/her. There is no informed consent for Phase III activities, we are asking for a waiver of documentation of consent for these activities.

Waiver of Consent/HIPAA Authorization Protocol (December 2020-)

Study recruitment materials will be mailed to individuals. Potential participants can choose to open the letter at a time that is appropriate for them. There are no recruitment or screening calls for this Phase. There is no informed consent for Phase III activities, we are asking for a waiver of documentation of consent for these activities.

10.2 Data Storage at KPWA**a. Storage Location**

Where will the data be stored?

All data will be stored on the KPWHRI secure network folders accessible only to research study team members.

Chart review data for ADWE's will be stored on KPWA's REDCap, behind the KPWA firewall.

b. Who Can Access Data?

Who will have access to the identifiers/linking file?

Only the KPWHRI study programmer will have access to the linking file. The KPWHRI study programmer, Research Specialist, and Project Manager will have access to identifiers so that they can recruit patients, mail out study materials, track patients who opt out of the study by refusing to allow their data to be accessed for use in this study and review their medical record in Epic for ADWE chart review.

c. Identifier/Link Destruction Date

When (month/year) will the identifiers, and the link to identifiers, be destroyed?

All identifiers will be destroyed 3 years after the end of the study which is 8/29/2026.

d. Other Security Measures

Describe any other steps that will be taken to ensure security (e.g., password protection, encryption, separation of identifiers from data, certificates of confidentiality, etc).

Computer files will be password protected with access restricted to staff using this information to perform study-related activities. All analytic data files will be password protected. Data tables with any identifiers needed for mailing the patient brochures (i.e., name, address) or recruitment into the focus groups (i.e., name and phone number) will be kept separate from all other study data tables. All employees at KPWHRI routinely sign a confidentiality form that covers access to all data encountered.

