At clinic roll-out, the KPWHRI Study Programmer will access KPWA automated data (VDW tables) and receive data files from STRIPE, SMART and COMET to identify the eligible Intervention Group (see section 3.3 for eligibility criteria). The KPWHRI Programmer loads the sample into the study database. Every month, the KPWHRI programmer updates the medication lists for the Intervention Group and runs an algorithm to select which patients in the Intervention Group are mailed to that month (see Figure in section 7.1.e on the selection of who is mailed to each month). The KPWA survey research program will print notification letters and relevant patient brochures and mail these materials to patients. At the same time, the Research Specialist will send the Epic Staff Message, a message letting the provider know their patient was included in the study and a link to the EBPO of the same medication class. In order to ensure that KP providers are not confused by this communication, we will inform providers at the Intervention Clinics about this study and materials that they can expect to receive through morning huddles and/or brown bag lunches as deemed appropriate by the clinic managers.

One month after the initial brochure is sent, the KPWA survey research program will send out the postcard mailer.

The same process of identifying the sample will occur for usual care clinics at the time the matched intervention clinic goes live, but the Control Group and their respective providers will not receive any of the educational materials.

Providers:

Providers are not subjects in this research. We are not screening or recruiting providers for this study.

Prior to clinic rollout, the research team will explain the study to providers at team huddles and meetings (whichever individual clinics prefer) and the information to be shared at these huddles/meetings has been uploaded in IRBNet.

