Adverse drug withdrawal events (ADWE) are possible side effects of our intervention if participants decide to taper their medications. For the purpose of safety monitoring, we will conduct medical record review to determine if any serious ADWE's occurred in our study population for both the intervention and usual care group in participants with prescriptions for opioids and/or benzodiazepines. We define serious as ADWE that require an emergency department visit or hospitalization.

☐ Data from another institution's patient medical records (**specify institution[s]**):
| |

- ☐ Individual medical charts
- ☐ Electronic warehouse/administrative data
- ☐ Other (explain): | |

☒ Data from a previous study

IF CHECKED, specify study title and principal investigator's name and IRBNet #; explain consent provisions; attach the previous consent form.

Data from the SMART and STRIPE studies will only be used to ensure that participants from those studies are excluded from being selected as participants in this study. Data will not be used for any other uses or analyses. Information on SMART and STRIPE below.

Systematic Multi-Domain Alzheimer's Risk (SMART). PI: [name]. IRBnet# 1220346

The consent process for SMART is:

- 1) SRP staff will administer oral informed consent on the phone for the following: to ask eligibility screening questions, to schedule an in-person baseline visit, and to mail an ActiGraph to be worn one week prior to the baseline visit.

- 2) At the start of the baseline visit, the research specialist will obtain written informed consent for measurement visits, HE contacts if applicable, and post-study activities.
- 3) If the participant is randomized to the SMARRT intervention arm, the health coach will mail a copy of the intervention addendum ahead of the first coaching contact. The coach will obtain written informed consent for intervention activities at the first coaching contact.
- 4) For both SMARRT and HE, if a participant shows possible signs of dementia, we will ask to conduct additional testing, as described in the main consent form.

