 - a. Sample created on the date the intervention is rolled-out (2 of the 9 clinics rolled out each month) to a particular intervention clinic and the matched usual care clinic
3. The study team mails the notification of study letter, first brochure, and relevant self-care handout(s) to a subgroup of the Intervention Group from each intervention clinic each month. The Control Group receives nothing.
4. Urls for corresponding EBPOs sent via Epic Staff Messaging to the patient's provider.
5. One month after sending the patient brochure, the study team mails the postcard mailer
6. Repeat process for subsample each month for 12-months.
 - a. Patients (and accompanying materials to their providers) receive only one brochure per medication class during the study period
 - b. Patients taking multiple medication classes of interest will receive no more than one brochure every 3 months for a max of 4 brochures in 12 months.

Collect deprescribing information.

1. Exploratory work: the KPWHRI study programmer will look in the CESR Med Order Table to ascertain availability of deprescribing information for all participants for the medications of interest.
2. Chart validation: the KPWHRI study programmer and project manager will conduct chart validation on a subset (up to 20%) of study participants to look for concordance between what is in the CESR Med Order Table and what is in the chart.
3. Refine code to collect deprescribing information based on #1 and #2 and pull data to assess outcomes at 24 months post-roll out into the intervention clinic.

Extract automated data from KPWA VDW on Intervention and Control Group to assess outcomes at 24 months post roll-out into the intervention clinic and matched usual care clinic.

Ascertain ADWE for the purpose of safety monitoring. We will conduct medical record review to determine if any serious ADWE's occurred in our study population for both the intervention and usual care group in participants with prescriptions for opioids and/or benzodiazepines. We define serious as ADWE that require an emergency department visit or hospitalization.

1. The study programmer will identify potential ADWEs using electronic data sources
2. The KPWA chart abstractor will review the medical records to ascertain if a serious ADWE occurred. They will enter information regarding the event into a chart abstraction tool in REDCap.

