3. The KPWA chart abstractor will send redacted medical record information about the event to [name] using the KPWA secure file transfer site. A material and data transfer agreement will be in place prior to sending this information
4. [name] will conduct her own independent review of the potential ADWE and enter the information into the chart abstraction tool in REDCap
5. At the end of chart redaction, the results of the double chart abstraction will be compared. Any discordance in outcomes will be adjudicated by a third party- [name].

8. Risks & Benefits

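### Review of serious withdrawal events is not masked to arm, and staff who send the intervention materials have access for that review

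*Combined protocol and SAP*

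**What the plan says.** Section 7.3.c presents ADWEs as possible side effects of the intervention. Serious cases, meaning those that need an emergency department visit or hospitalization, are to be found by record review "for both the intervention and usual care group in participants with prescriptions for opioids and/or benzodiazepines". The waiver-protocol table in 7.3.d lists ADWE codes among the outcome diagnoses and names ADWEs with falls, crashes and overdose as outcomes.

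Section 7.5 sets out the process:
- Candidates: "The study programmer will identify potential ADWEs using electronic data sources".
- First reading: "The KPWA chart abstractor will review the medical records to ascertain if a serious ADWE occurred".
- Packet for the second reviewer: "The KPWA chart abstractor will send redacted medical record information about the event", by secure transfer and under a data transfer agreement.
- The second reviewer classifies independently, and a third party settles discordant cases.

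Section 10.2.b describes access differently: "The KPWHRI study programmer, Research Specialist, and Project Manager will have access to identifiers so that they can recruit patients, mail out study materials". The same sentence goes on to opt-out tracking and ends with permission to "review their medical record in Epic for ADWE chart review". Under section 5.2.a (waiver protocol), "the Research Specialist will send the Epic Staff Message" to the patient's provider at the time of the mailing.

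Section 7.1.a allocates by clinic and lists the nine intervention and nine control clinics by name.

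**The concern.** The hospital contact is a matter of record, but calling it a withdrawal event is a judgement. The plan treats it as one by requiring two readings and adjudication. Someone who knows that a deprescribing brochure went out may read tremor, anxiety or pain as withdrawal more readily. Someone invested in the programme may do so less readily. The direction cannot be predicted, but in either case part of a difference between arms would come from knowing the allocation.

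The stake is the credibility of the one harm that the plan adjudicates. Sections 9.2 and 9.3 plan neither a data safety monitoring plan nor a monitoring board, so this review is the only harm-specific assessment described. Delivery of the intervention cannot be blinded, but classification of events can be masked to a useful degree.

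**Working it through.** The plan gives no ADWE rate, candidate count or power figure, so there is nothing to reproduce. The check is mainly a comparison of sections.

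**Who can know the arm at each step**

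1. *Candidate finding (7.5).* The programmer searches electronic data in both groups. No judgement of attribution is described here.
2. *First reading (7.5).* The abstractor sends out the redacted material, and so works from the unredacted record. That record can show the clinic. Read against the list in 7.1.a, the clinic gives the arm. Masking is not mentioned.
3. *Access (10.2.b).* Three roles have access for ADWE chart review, and the same sentence covers mailing. Controls receive no materials (7.5), and the Research Specialist sends the provider messages (5.2.a), so these staff can know who was mailed. The abstractor of 7.5 is not on the list. The abstractor may be one of the three or someone else, and the sections do not say.
4. *Second reading (7.5).* The packet is redacted, but its content is not defined. The redaction appears beside the secure transfer and the transfer agreement, which reads as a privacy step. Masking is not stated.
5. *Adjudication (7.5).* Discordant cases only. Masking is not stated.
6. *Notes that mention the study.* Under 7.1.i, study information is not filed in the medical record. But the materials are meant to prompt a conversation between patient and provider (7.1.e), so a clinician's own note may mention the brochure.

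**What the double-review structure does to a shift (all inputs assumed)**

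Let p1 and p2 be the chances that the first and second readers confirm a candidate, and a the chance that the adjudicator confirms a discordant one. Readings are taken as independent. Then

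P(confirmed) = p1·p2 + [p1(1 − p2) + p2(1 − p1)]·a.

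Assume no true difference between arms, and 0.5 for every reader in usual care: 0.25 + 0.50 × 0.5 = 0.50. Let knowledge of arm move a reader to 0.6 in the intervention arm.

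- First reader only: 0.30 + 0.50 × 0.5 = 0.55; ratio 0.55/0.50 = 1.10.
- First reader and adjudicator: 0.30 + 0.50 × 0.6 = 0.60; ratio 1.20.
- All three: 0.36 + 0.48 × 0.6 = 0.648; ratio 0.648/0.50 = about 1.30.

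The first line also bears on the remedy. Even with the second reader and adjudicator unaffected by arm, a ratio of 1.10 remains, because the first reading still enters the result. It disappears only if the reported classification rests on masked readings alone.

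**The case against.** The strongest reply is that silence about masking is not evidence that reviewers know the arm. Section 7.5 gives the judgement to an abstractor, an independent second reviewer and a third party, and none is said to know the allocation. Section 10.2.b answers a question about access to identifiers. It does not say that the three roles classify events, or which role does which task. A reader might infer that mailing staff decide which events count. The documents do not say so. What stands is that 10.2.b permits those staff to take part and does not match 7.5.

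A reader might also infer that a formal safety comparison is compromised. The stated purpose is safety monitoring, and the analysis plan in 2.2.d specifies no ADWE test. That limits the claim. Still, 7.3.d lists ADWEs among outcomes, and the main use of reviewing usual care is as a comparator.

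The redaction may already do part of the work. Section 11.1 says that no one outside KPWA receives the identifiers in 11.2, which include names and geographic units smaller than a state. That could catch some clinic names. Whether it covers clinic and provider names is not explicit, and no item on the list covers mention of the study or its brochure. It would not affect the first reading in any case. The chart abstraction form is marked as attached but is not in the text available here, so masking instructions may exist there.

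The emergency visit or admission requirement limits discretion, and double review dilutes one reader's lean. Both points stand. It would be tempting to picture a single reviewer confirming 30% against 20%, say 9 of 30 charts against 6 of 30, and to report a ratio of 1.5. Those figures are invented and leave out the other two readers. With 30% against 20% for the first reader only, 20% for the second, and an adjudicator confirming 20% to 50% of discordant cases, the formula gives 0.136/0.104 = 1.31 to 0.25/0.20 = 1.25.

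**Conclusion.** The concern holds as a gap in the plan. Serious ADWEs are a judged safety outcome sought in both arms, and no part of their review is stated to be masked. The first reading is made from a record that can show the arm, and access extends to staff who send the intervention materials. Any contrast of ADWEs between arms could be shifted in either direction.

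The size cannot be estimated from the documents. The ratios of 1.10 to 1.30 rest on assumed confirmation rates and independent readings, and show only that the existing double review reduces a shift without removing it. The documents do not support a claim that the reviewers are known to be unmasked, or that a prespecified comparison is biased by a given amount. The point merits action because the change is cheap and uses roles already in the plan.

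**What to change.** In the ADWE steps of 7.5 and in 10.2.b:

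1. State who reviews and make the two sections agree. Keep anyone who does mailings or provider messages out of event classification.
2. Have the programmer issue candidate charts from both arms, mixed, under neutral IDs.
3. Extend the existing redaction to clinic, provider names and any mention of STOP-FALLS, the brochure, the EBPO or the mailing.
4. Have the second reviewer and the adjudicator classify from the masked packet only, and use that masked classification for any report of ADWEs by arm. State how their readings combine, so that the abstractor's unmasked reading does not enter the reported result.
5. If the attached abstraction form already contains masking instructions, refer to them in 7.5.

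The cost is protocol wording and more redaction time per candidate chart. No new roles are needed, although the adjudicator's workload grows if more than the discordant cases are read. Some clinical context will be lost. Masking may remain incomplete, because the taper history needed to judge withdrawal can itself hint at the arm.
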